## Sample size estimation

### *Between-group effects (intervention vs usual care)*

Required sample size was estimated by using effect sizes of a previous pilot study that demonstrated a mean change in CRF  $3.6 \pm 3.2 \text{ ml.kg.min}^{-2}$  (REF 16/WA/0231) and existing epidemiological evidence. A change in cardiorespiratory fitness of  $3.5 \text{ ml.kg.min}^{-2}$  has been deemed clinically meaningful with an associated reduction in all-cause mortality (13%) and cardiovascular disease risk (15%; Lee et al., 2010). Yet, it has also been demonstrated that small increases in fitness (Males:  $0.5 \text{ ml.kg.min}^{-2}$ ; Females  $1.0 \text{ ml.kg.min}^{-2}$ ) are associated with significant reductions in clustered-cardiometabolic risk in at-risk individuals (Simmons et al., 2008).

Therefore, we decided a moderate-large effect size (based on pilot baseline CRF SD of  $3.2 \text{ ml.kg.min}^{-2}$  equivalent to a change of  $1.98 \text{ ml.kg.min}^{-2}$ , would be clinically meaningful. This is between the clinically meaningful change of 3.5 units reported by Lee et al. (2010) and the smaller increases of 0.5 to 1 unit reported by Simmons et al. (2008) in at-risk individuals. Thus, to detect a difference of 1.98 units ( $\text{ml.kg.min}^{-2}$ ) between groups, it was estimated that a total sample of 84 would be needed ( $f=0.25$ ,  $p=0.05$ , power = 0.8). Factoring for dropout witnessed in the pilot study (40%) this yields a sample of 140 patients (70 per ERS arm).

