## Research Protocol

The proposed research study is part of a PhD that is taking a phased approach (MRC, 2008) to develop, pilot, and evaluate an exercise referral scheme (ERS) for inactive individuals with health conditions. Study 1 [REF 16/EM/0157] involved the co-development of the intervention in collaboration with a multidisciplinary steering group (e.g. researchers, GP's, commissioners etc.). Study 2 (REF 16/WA/0231) explored the feasibility of the ERS and tested potential outcome measures to inform a subsequent evaluation trial. **Study 3 (this application) will be a pragmatic, quasi-experimental trial to test the effectiveness of the ERS.** The research will be conducted in collaboration with Liverpool NHS Clinical Commissioning Group (CCG) and Liverpool City Council (LCC). **This protocol relates to study 3 only.**

**Formal study title:** “Clinical and cost-effectiveness of a co-developed, evidence-based physical activity referral scheme for the treatment and prevention of health conditions: a pragmatic trial”

**Lay study title:** “Evaluation of a co-developed physical activity referral scheme”

**Aim:** *To test the pragmatic effectiveness and cost-effectiveness of a co-developed, evidence-based physical activity referral scheme, with embedded process evaluation.*

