### **Objectives:**

- To investigate the relative effectiveness (for improving cardiorespiratory fitness at 12 weeks) and cost-effectiveness (PA levels at 6 months) of two delivery modes of ERS (1. co-developed physical activity referral scheme; 2. standard ERS)
- To explore who each intervention reaches, patient adherence levels, fidelity of intervention delivery and acceptability of the intervention to patients and staff.

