### 2. ERS staff

#### *Inclusion Criteria:*

- Qualified exercise referral practitioner (ERP)
- Involvement in the delivery of the ERS at Centre A (intervention) or Centre B (usual care)

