## Recruitment

### ***Intervention and usual care conditions***

Eligible patients will be recruited from Centre A and Centre B (after they have been referred to the ERS by a health professional). Once referred, it is standard protocol that ERS patients visit their chosen *Lifestyles* fitness centre to book an ERS induction with administrative staff. During this initial contact, administrative staff will introduce the study briefly and provide the individual with a summary poster (attached). If the patient is interested, administrative staff will gain verbal consent to pass the patient's contact details to the researcher (NB this is consent for sharing details only, the participant will still have the opportunity to opt out before full research consent is sought). Administrative staff will then provide patients with the participant information sheet to take away and have some time to consider. Patients will be informed that the researcher will contact them within one week to discuss the study and check if they want to take part. Researcher contact details will be provided on the poster and information sheet in case the participant has any questions in the meantime.

For patients who consent to speak to the researcher, the administrative staff will book an ERS induction 2-3 weeks later (to allow time for the patient to undergo baseline testing prior to starting the ERS). The researcher will then contact the patient to arrange a visit to Liverpool John Moores University (LJMU) laboratories for baseline collection of health measures.

Patients who opt out of the study at this stage will continue with the ERS as usual.

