#### ***No treatment control condition***

Participants in the no treatment control group will be recruited via posters placed around LJMU, electronic invitations on LJMU research recruitment websites, email communications to LJMU staff and students, and LJMU social media output (see attached documents). Interested participants will contact the researcher for further information, who will e-mail them a full participant information sheet. If the participant then decides to take part the researcher will arrange a date and time to visit LJMU laboratories for baseline collection of health measures.

**Participant blinding.** Due to the nature of the study, it will not be possible to fully blind patients to their study condition (as they will know whether they are signed up to attend an ERS or not) or to blind ERS staff (who will know whether their centre is the intervention or the usual care condition). Patients within the two active conditions (intervention and usual care) will not however be informed whether their centre is the intervention or the usual care condition.

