#### **Conditions**

##### ***Intervention (Centre A)***

[figure not shown]
Both the co-developed scheme and standard ERS offer subsidised access to a fitness centre for 12 weeks. However, in addition to this the co-developed intervention (centre A) will offer:

- more physical activity options that include both daily opportunities to increase PA and activities available at the fitness centre;
- more individual progress meetings, during which the GP exercise referral practitioner will provide behaviour change support (Week 0, 4, 8, 12 and 18); and
- more efforts to refer patients to optional additional support from a 'Health Trainer' service qualified to provide advice on multiple health-related behaviours.

These adaptations are in line with the current NICE guidelines as well as a local evaluation study that fed into the development of the scheme. The aim of the co-developed ERS is a person-centred approach to improve overall well-being and quality of life through PA. As the intervention is drawing on an existing scheme, delivered/guided by qualified ERPs, and has been developed by a multidisciplinary stakeholder group involved with the existing scheme, it is deemed that there are no additional risks to the users compared to the existing

scheme in operation. The key aspect of the intervention is that the participant has choice but is supported through the process.

It was found during the pilot study that some patients were referred inappropriately to the ERS who were already active or were seeking subsidised access to certain activities (e.g. swimming) without a need for additional behaviour change support. In an attempt to provide more targeted support, patient eligibility for the ERS will be explored through the patient-centred induction. If it is deemed by both the instructor and patient that the intensive 18-week intervention is not the most appropriate for the patient's needs, alternative options will be offered (see figure 1). Since this study aims to investigate the real-world effectiveness of an ERS that is tailored to patient needs, patients referred to the ERS at Centre A who opt not to take part in the 18-week intervention will remain in the research study (i.e. an intention to treat approach).

**Figure 1.** Co-developed referral scheme that will run at Centre A (intervention centre).

[figure not shown]

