## **Measures**

### **Demographic measures**

Demographic measures collected at baseline will include: date of birth, sex, postcode, employment status, ethnicity, referral reason, referring professional, and number of previous referrals.

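### Each ERS condition runs at a single patient-chosen centre, so the stated power and 5% level apply at most to Centre A versus Centre B, not to the scheme effect named in the aim and objectives

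*Combined protocol and SAP*

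**What the plan says.** The Research Protocol section says the study "will be a pragmatic, quasi-experimental trial to test the effectiveness of the ERS". The first objective is "To investigate the relative effectiveness (for improving cardiorespiratory fitness at 12 weeks" for two delivery modes of ERS. Both are claims about the scheme.

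The conditions are tied to centres. The staff inclusion criterion reads "Involvement in the delivery of the ERS at Centre A (intervention) or Centre B (usual care". Under Intervention (Centre A), both schemes give 12 weeks of subsidised access, and "in addition to this the co-developed intervention (centre A) will offer" further components. Standard ERS is described only under Usual care (Centre B). Patients reach a centre by choice: "Once referred, it is standard protocol that ERS patients visit their chosen" fitness centre. The sample size section expects 4-5 practitioners at A and 2-3 at B.

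The same section sizes the comparison from a difference of 1.98, an SD of 3.2, p = 0.05 and power 0.8: "it was estimated that a total sample of 84 would be needed", then 140 after 40% dropout. The Analyses section plans linear mixed models with treatment, time and their interaction at P < .05. It leaves the covariates open apart from baseline values. Neither section mentions a centre effect or limits what the test can show.

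**The concern.** A power statement and a significance level belong to a particular comparison. Here the data compare patients at one centre with patients at another, while the aim and objective speak of the scheme. The two coincide only if nothing else about the centres (staff, facilities, catchment, who chooses to attend) affects 12-week fitness. The plan does not state that assumption.

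At stake is the main conclusion. A difference between centres could be reported as a benefit of the co-developed scheme when the schemes are equal, or could hide a real benefit. The economic evaluation takes 6-month effectiveness data on physical activity into a lifetime model, and the same confounding would be carried forward there as a scheme effect.

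**Working it through.** **Inputs.** From the sample size section: difference 1.98, SD 3.2, 5% level, power 0.8, total 84 (42 per arm), 40% dropout. A two-sided test is assumed, because sidedness is not stated. From the recruitment and conditions sections: one centre per ERS condition. Assumed: centre differences of 0.5, 1.0 and 1.5 units. The first two equal the small fitness gains named in the sample size section, where they are health-related gains and not estimates of how centres differ.

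**1. The plan's figure.** For a two-group t-test with 42 per arm (82 df), the standardised difference is 1.98/3.2 = 0.619 and SE = 3.2 × √(2/42) = 0.698. Power is 0.800, so 84 reproduces, and 84/0.6 = 140. The calculation treats patients as independent and has no centre component.

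**2. Identifiability.** Two centres in two conditions leave 2 − 2 = 0 degrees of freedom for variation between centres. A centre term would be collinear with arm. This holds whatever the size of the centre difference.

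**3. Equal schemes, centre difference c that baseline fitness does not explain.** The probability of P < .05 is the power of the same test at c/3.2:

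| c (units) | 0.5 | 1.0 | 1.5 |
|---|---|---|---|
| P(significant) | 0.109 | 0.293 | 0.565 |

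**4. True scheme effect 1.98, Centre A lower by c for other reasons.** The expected difference is 1.98 − c:

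| c (units) | 0 | 0.5 | 1.0 | 1.5 |
|---|---|---|---|---|
| Expected difference | 1.98 | 1.48 | 0.98 | 0.48 |
| Power | 0.800 | 0.554 | 0.284 | 0.104 |

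Steps 3 and 4 keep the plan's SD of 3.2. The plan labels it a baseline SD but also prints 3.2 beside the pilot mean change. A different residual SD would change the figures.

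**5. A stable fitness difference, present equally at baseline and week 12.** Take 3.2 as the SD at both visits and assume a correlation of 0.7. Baseline adjustment leaves (1 − 0.7) × c = 0.15, 0.30 or 0.45 units. The residual SD is 3.2 × √(1 − 0.7²) = 2.285, so SE = 2.285 × √(2/42) = 0.499. With equal schemes, P(significant) is about 0.060, 0.091 and 0.145. The planned adjustment therefore removes most of this route, and what remains is centre, staff and case-mix effects on change.

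**The case against.** The strongest reply is that the plan is open about its design. It calls itself pragmatic and quasi-experimental and labels condition by centre throughout. This discloses the lack of randomisation, but neither the power statement nor the analysis says what one centre per condition does to the inference.

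Other parts of the plan soften the problem:

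- Patients in the two ERS arms "will not however be informed whether their centre is the intervention or the usual care condition". This limits choosing a centre for its condition, but not differences in catchment or case mix.
- Baseline values enter the models, which largely deals with stable fitness differences (step 5). This part of the objection stands.
- Attendance and fidelity are recorded at both centres. They describe delivery but cannot identify the effect.
- Practitioner support is part of the intervention, so not every staff difference is nuisance. This is also fair, but the data cannot tell the two kinds apart.

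A reader might infer more than the documents support. They do not show that the centres differ, nor by how much, so no actual error rate can be stated. The total of 84 is not miscalculated for 1.98 and 3.2; the printed f = 0.25, at which 84 patients give power 0.62, is a separate matter. Nor is it true that more patients never help. In the masking case of step 4, 70 evaluable per arm would raise power from 0.55, 0.28 and 0.10 to 0.78, 0.44 and 0.14. More patients still cannot separate scheme from centre.

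**Conclusion.** The point holds as a limit on inference. The 80% power and 5% level apply at most to patients at Centre A versus patients at Centre B. They carry over to the scheme only if the centres differ in nothing else that affects 12-week fitness. That conclusion follows from the design alone and needs no assumed figure.

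The size is illustrative. With equal schemes, a significant result has probability 0.11 to 0.56 for unexplained centre differences of 0.5 to 1.5 units, and power for a true 1.98 falls to between 0.55 and 0.10 when such a difference runs against Centre A. For a stable baseline difference of the same size, the probability after adjustment is only about 0.06 to 0.15. The concern covers the intervention versus usual care comparison. It does not make the two-centre design unusable; it calls for a conclusion that matches the design.

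**What to change.** Keep the design and N.

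1. In the sample size section, add: *The power and 5% significance level apply to the comparison of patients at Centre A with patients at Centre B. Reading this difference as an effect of the scheme further assumes no other difference between the centres that affects 12-week fitness.*
2. In the aim, the objective and the Analyses section, word the comparison and primary conclusion as Centre A (co-developed scheme) versus Centre B (standard ERS). State that scheme, centre, staff and self-selection effects cannot be separated. Carry the same limit into the economic model.
3. Optional and partial: fit the two-arm ERS comparison as a separate model, adjusted for baseline fitness and a short set named in advance. The demographic data already include "date of birth, sex, postcode, employment status, ethnicity, referral reason, referring professional, and number of previous referrals". Age, sex, employment status and grouped referral reason would be one choice; about 84 evaluable patients cannot support many terms. A separate model is needed because controls are recruited through the university and have no referral data. State that this addresses measured self-selection only.

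Items 1 and 2 cost wording and a more modest power statement and conclusion. Item 3 costs one extra model and a few degrees of freedom. None needs new patients or new data.

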### *Between-group effects (ERS arms vs no treatment control)*

It is estimated that a larger effect size would occur between the ERS arms and the no treatment control, it was therefore decided we did not need to recruit as many participants. To identify a difference of 3.2 units ( $\text{ml.kg.min}^{-2}$ ; 0.3 units smaller than the within-subjects change seen in the previous pilot for fitness to allow for some variance) between the ERS arms and a no treatment control arm a sample of 17 would be required ( $f=0.5$ ,  $p=0.05$ , power = 0.8). Factoring for dropout witnessed in the pilot study (40%) this yields a sample of 30 patients for the no treatment control arm.

In summary, the study will aim to recruit 70 patients for the intervention condition, 70 for the usual care condition and 30 for the no treatment control.

*ERPs.* All ERPs responsible for delivering the ERS at Centre A (n=4-5) and Centre B (n=2-3) will be invited to take part.

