### ***No treatment control***

These participants will receive a lifestyle advice booklet only (provided to all groups at the baseline data collection point).

**Figure 2.** Overview of intervention measure time points for each arm.

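### Is the no-treatment control arm too small because its 3.2-unit target comes from a before-after change in the pilot?

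*Combined protocol and SAP*

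**What the plan says.** Under Sample size estimation, the subsection on intervention versus usual care starts from the pilot: "Required sample size was estimated by using effect sizes of a previous pilot study that demonstrated a mean change in CRF" of 3.6 with an SD of 3.2. It settles on 1.98 units, which it says "would be clinically meaningful. This is between the clinically meaningful change of 3.5 units" from one cited source and the 0.5 to 1 unit from another. It then sizes the two ERS arms: "Thus, to detect a difference of 1.98 units" it asks for 84 completers in total, or 140 recruited after 40% dropout.

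The next subsection, on the ERS arms versus no treatment, expects a larger effect, so "it was therefore decided we did not need to recruit as many participants". The target is 3.2 units, explained as "0.3 units smaller than the within-subjects change seen in the previous pilot for fitness to allow for some variance". For a difference of that size "between the ERS arms and a no treatment control arm a sample of 17 would be required", with f = 0.5, a 5% level and 80% power. Allowing for 40% dropout, this becomes 30.

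Three other places matter. The Objectives name only the comparison of the two ERS delivery modes. The No treatment control section says of the controls, "These participants will receive a lifestyle advice booklet only", and adds that every group gets this booklet at baseline. The Analyses section specifies linear mixed models across all three arms with baseline values as covariates.

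**The concern.** A mean change within treated patients equals a treatment-control difference only if untreated people do not change at all. Controls in this trial repeat the submaximal test at week 12 and may improve through familiarity or through volunteering for a health study. The documents report no control-group change from the pilot, and the 0.3-unit deduction is described as an allowance for variance, not for change in controls. Centre A patients who opt out of the 18-week programme also stay in the analysis, which could dilute the effect.

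The plan also appears to apply two standards. It treats 1.98 units as worth detecting between the ERS arms, yet sizes the control arm for a difference about 1.6 times as large (3.2/1.98 = 1.62). If the two ERS arms turn out alike, the control arm is the only evidence on whether either scheme works. A true benefit of 1.98 units over no treatment would then be missed about four times in ten against one arm, or one time in three against the pooled arms, before baseline adjustment.

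**Working it through.** **Inputs, all from Sample size estimation.** SD 3.2; differences 3.2 and 1.98; 40% dropout; 70, 70 and 30 recruited. Expected completers are 70 × 0.6 = 42 per ERS arm (84 pooled) and 30 × 0.6 = 18 controls. The plan does not state sidedness; a two-sided 5% test reproduces its figures. Power is from the noncentral t distribution with noncentrality δ / (SD × √(1/n₁ + 1/n₂)).

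**The plan's own figures.**
- Control arm: d = 3.2/3.2 = 1.0, that is f = 0.5. With 17 per group power is 80.7%; with 16 it is 78.1%. So 17 reproduces. 17/0.6 = 28.3, which rounds up to 29; the plan's 30 is slightly generous.
- ERS arms: 42 v 42 at 1.98 gives 80.0%, so SD 3.2 is the plan's working value there too. (84 follows from 1.98/3.2, f = 0.31, and not from the printed f = 0.25. That is a separate matter and does not enter here.)

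**Power delivered at the stated target of 3.2.** The plan computed 17 v 17, but the ERS groups are larger.
- One ERS arm v control: SE = 3.2 × √(1/42 + 1/18) = 0.901; noncentrality 3.2/0.901 = 3.55; power 94%.
- Pooled: SE = 3.2 × √(1/84 + 1/18) = 0.831; noncentrality 3.85; power 97%.

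**Margin before 80% is lost, unadjusted.** The smallest difference with 80% power is 2.57 units (one arm) or 2.35 (pooled). Measured from the pilot's 3.6, control change and dilution together can take 3.6 − 2.57 = 1.03 units (one arm) or 3.6 − 2.35 = 1.25 (pooled). Measured from the plan's 3.2, the room is 0.63 or 0.85. The documents give no figure for the change to expect in controls.

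**Power at 1.98, unadjusted.** 42 v 18: 1.98/0.901 = 2.20, power 58%, 95% CI half-width 1.80. Pooled: 1.98/0.831 = 2.38, power 66%, half-width 1.65. Reaching 80% would take 42 control completers (42/0.6 = 70 recruited) against one arm, or 28 (28/0.6 = 46.7, so 47) against the pooled arms.

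**With the planned baseline adjustment.** The text gives 3.2 both as the spread of the pilot change and as the "based on pilot baseline CRF SD of" 3.2. If both hold and the week 12 SD is the same, SD²(change) = 2 × SD² × (1 − r) gives r = 0.5. The adjusted SD is 3.2 × √(1 − 0.5²) = 2.77. With one degree of freedom lost:

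| | One arm (42 v 18) | Pooled (84 v 18) |
|---|---|---|
| Power at 1.98 | 70% | 78% |
| Difference with 80% power | 2.22 | 2.04 |
| Controls recruited for 80% at 1.98 | 44 | 34 |

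The correlation is inferred, not stated. If 3.2 is the SD of change only, assumed correlations from 0.5 to 0.9 give 70% down to 60% (one arm) and 78% down to 68% (pooled). If 3.2 is a baseline SD only, 80% at 1.98 is reached at about r = 0.64 (one arm) or 0.54 (pooled).

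**A clerical slip.** 3.2 + 0.3 = 3.5, whereas the pilot change is given as 3.6. The 0.1-unit mismatch does not affect the calculation, which uses 3.2.

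**The case for a change.** The best case for a change is that the assumption, not the arithmetic, is at fault. An uncontrolled change is a poor guide to a controlled difference and usually overstates it. Power of 94% at 3.2 is little comfort if the true difference is nearer 2. The contrast has its own sample size statement and is part of the model for every outcome, so its power claim should rest on something firmer. Baseline adjustment does not clearly rescue it: at r = 0.5, power at 1.98 is still under 80%.

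Much of this stands. The derivation is weak, the pooling of the ERS arms is left open, and at 1.98 units the contrast is underpowered on most readings of the SD. Two supporting arguments are weaker than they look. The booklet goes to all groups, so it need not narrow the difference between them. As for dilution, the protocol says the pilot itself met inappropriately referred patients, some already active, so the 3.6 may not come from a purer population.

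What does not stand is the step to 70 or 47 controls. That applies a target chosen for two active schemes to a contrast where the plan openly expects more. Planning different contrasts around different expected effects is ordinary practice. The same section also cites 3.5 units as clinically meaningful, and both detectable differences, 2.57 and 2.35, lie below it.

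**Conclusion.** No change is needed. The plan misses no figure that it states: it claims 80% power at 3.2 units and delivers 94% (97% pooled), with 80% kept down to about 2.6 units (2.4 pooled) unadjusted, or about 2.2 (2.0) at a baseline correlation of 0.5. The 58% and 66% at 1.98 are correct, but they answer a question the plan did not set for this contrast and leave out the baseline adjustment that it does plan.

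Enrolling 17 to 40 more controls (47 − 30 and 70 − 30) would buy little. Controls are university volunteers and ERS participants are referred patients, without randomisation. A larger control arm narrows the interval but leaves that difference in place. The main comparison of the two ERS modes is untouched. Saying whether the arms are pooled, or which SD is meant, would be tidy but would change no result, and analysts can settle both when they fit the model.

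This rests on SD 3.2, 40% dropout in every arm and a two-sided 5% test. The 40% comes from the pilot of the scheme and may not apply to controls who attend no scheme. The consequence for readers is one of interpretation: a non-significant ERS-control difference would not rule out a benefit near 2 units, since the unadjusted 95% interval extends about 1.8 units either side (1.65 pooled).
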